1 PROTOCOL SUMMARY

1.1 SYNOPSIS

| | |
|---|--|
| Title: | Modulation effects of a novel body-mind intervention on subjective cognitive decline |
| Grant Number: | R61AT010138-02S1 |
| Study Description: | The study aims to understand the mechanisms and training effects of evidence-based body-mind training on improving cognitive performance and preventing cognitive decline. Specifically, it aims to investigate the modulation effects of a novel body-mind intervention on subjective cognitive decline (SCD) using an evidence-based preventive intervention - integrative body-mind training (IBMT). |
| Objectives: | Primary Objective: This study aims to investigate the modulation effects of a novel body-mind intervention on behavioral and cognitive outcomes. Secondary Objectives: This study aims to investigate the modulation effects of a novel body-mind intervention on brain outcomes. |
| Endpoints: | Primary Endpoint: Behavioral and cognitive outcomes Secondary Endpoints: Brain outcomes |
| Study Population: | 40 adults (both sexes) between the age 40-65 years old with SCD in the Phoenix, AZ area. |
| Phase or Stage: | N/A |
| Description of Sites/Facilities Enrolling Participants: | The participating site/facility is Arizona State University, where enrollment of participants happens. There is no foreign site. |
| Description of Study Intervention/Experimental Manipulation: | Experimental manipulation is evidence-based preventive intervention - integrative body-mind training (IBMT) and will be offered as a group for 10 sessions. |
| Study Duration: | 12 months |
| Participant Duration: | 3 months |

1.2 SCHEMA

Figure 1. Flowchart of screening, inclusion, and assessment process

1.3 SCHEDULE OF ACTIVITIES

| | Screening | Visit 1 Day 1 | Visit 2 to Visit 11 Day 3 ±1 to Day 12 ±1 | Visit 12 Day 13 ±2 | Visit 13 Day 90 ±2 |
|---|-----------|------------------|--|-----------------------|-----------------------|
| Review Eligibility | X | | | | |
| Informed Consent | | X | | | |
| Demographics | | X | | | |
| Outcome Evaluation | | | | | |
| Behavioral Assessment (Emotion Regulation Questionnaire; Five Facet Mindfulness Questionnaire; Subject Cognitive Decline Questionnaire) | | X | | X | X |
| Brain Assessment (MRI scan) | | X | | X | X |
| Randomization | | X | | | |
| Control & Experimental Interventions | | X | X | | |
| Adverse Events Reporting | | X | X | X | X |

2 INTRODUCTION

2.1 STUDY RATIONALE

More than five million people in the US have Alzheimer's Disease (AD), at a cost to society of more than \$200 billion per year. However, available preventions and treatments have limited efficacy. It is imperative to develop evidence-based programs to help promote cognitive functioning in older adults. We propose to address this urgent and critical public health issue by examining the effectiveness of a brief evidence-based mindfulness intervention – Integrative Body-Mind Training (IBMT) in old adults with SCD through randomized clinical trials (RCTs). We will examine if the intervention can improve behavioral and cognitive functioning, as well as brain changes in these older adults. Outcomes from this study will inform prevention and treatment option to promote health and well-being for individuals with SCD, MCI, and ADRD.

2.2 BACKGROUND

Subjective cognitive decline (SCD), the self-reported perception of memory or cognitive problems, is a risk factor for the development of clinical cognitive decline such as MCI and ADRD. Since SCD manifests prior to the onset of clinical impairment, it might provide an optimal stage of time at which to intervene with preventive therapies for ADRD before the progressive neurological loss and irreversible cognitive impairment.⁴⁹⁻⁵² Recently, few mind-body interventions such as Tai Chi and mindfulness suggested promising effects in preventing cognitive decline. However, these interventions often require longer training time to achieve modest benefits, making them less optimal for old adults to rapidly learn and achieve desirable outcomes.⁵³⁻⁶³ Thus, choosing short-term effective interventions in improving targeted outcomes is highly critical for this time-sensitive aging cohort. Moreover, most mindfulness studies on cognitive decline are cross-sectional, which are highly susceptible to confounds and noises.⁷³⁻⁷⁵ Previous SCD studies showed brain functional and structural abnormalities are associated with clinical progression and annual decline on executive functioning, attention, memory, and global cognition.⁶⁶⁻⁷² Self-control and attention deficits can be improved through brief intervention. Our preliminary RCTs in healthy adults provide support for our clinical trial by showing improvement in self-control, attention, cognitive functioning, emotion, stress reduction, and quality of life following brief IBMT intervention,¹⁻⁴⁵ suggesting its potential effectiveness in older adults with SCD.

2.3 RISK/BENEFIT ASSESSMENT

2.3.1 KNOWN POTENTIAL RISKS

The study includes behavioral, cognitive, and brain assessments, as well as mindfulness-based intervention.

Behavioral and Cognitive Assessments

- *Immediate risks: Potential boredom from completing the questionnaires and interviews.*
- *Long-term risks: Data including self-report, questionnaires and interview involve risk of breaches in confidentiality.*
- *Alternative procedures: There are no other available alternative procedures to assess behavior and cognition, since to assess the behavior and cognition, we have to use the actual assessments. To minimize immediate risks, breaks in between questionnaires and interviews are offered to reduce*

boredom. To minimize long-term risks, all information about the specific individuals will be maintained as confidential. Absolutely no names of subjects are used in published reports or in presentations in scientific meetings. All data will be kept in locked files and digital media in the PI's laboratory. Reference to individual subject data will be made with a number and letter code for each subject. Any risks to participants are minimal and are outweighed by the benefits of increasing our scientific understanding of improving cognitive function in older adults.

Brain Assessments

- *Immediate risks: Potential boredom from completing the MRI scan, the possibility of becoming uncomfortable in the enclosed space of the scanner.*
- *Long-term risks: MRI data involves risk of breaches in confidentiality.*
- *Alternative procedures: There are no other available alternative procedures to brain, since to assess the brain, we have to use the actual MRI assessments.*

Mindfulness-based Intervention

- *Immediate risks: Potential boredom from completing the intervention.*
- *Long-term risks: No known risk based on our previous studies ¹⁻¹².*
- *Alternative procedures: There are no other available alternative procedures, since the goal is to test the effects of the mindfulness-based intervention. To minimize immediate risks, breaks during the session are offered to reduce boredom.*

2.3.2 KNOWN POTENTIAL BENEFITS

Immediate potential benefits

The immediate potential benefits from participant in this study include that participants generally find the experimental paradigms enjoyable (i.e. meditation state) during the intervention sessions ^{2, 19-21}.

Long-term potential benefits

The long-term potential benefits include that participants have the opportunity to learn more about approaches and methods of improving attention, cognition, emotion and quality of life during the intervention and may be able to apply the learned knowledge in their everyday life.

2.3.3 ASSESSMENT OF POTENTIAL RISKS AND BENEFITS

Because this is a study that examines the effects of an intervention on behavior, cognition, and behavior, it is inevitable to expose participants to risk of boredom during their assessments and interventions, as these assessments and intervention are necessary for us to evaluate the effects of the intervention.

To minimize immediate risks of potential boredom from completing the behavioral and cognitive assessments, brain assessments, and mindfulness-based intervention, breaks during the assessments and interventions are offered to reduce boredom and give participants time to rest. To minimize long-term risks, all information about the specific individuals will be maintained as confidential. Absolutely no names of subjects are used in published reports or in presentations in scientific meetings. All data will be kept in locked files and digital media in the PI's laboratory. Reference to individual subject data will be made with a number and letter code for each subject.

Based on the risks of boredom and breach in confidentiality, as well as our approaches to minimize these risks, we conclude that any risks to participants are minimal and are outweighed by the benefits of increasing our scientific understanding of improving cognitive function in older adults, as well as the benefits of potentially having the participants learning ways to improve attention, cognition, emotion and quality of life in their everyday life.

3 OBJECTIVES AND ENDPOINTS

| OBJECTIVES | ENDPOINTS | JUSTIFICATION FOR ENDPOINTS |
|--|---|--|
| Primary | | |
| This study aims to investigate the modulation effects of a novel body-mind intervention on behavioral and cognitive outcomes. | Baseline and post-intervention assessments of behavioral and cognitive outcomes (emotion regulation, mindfulness, SCD). | The novel body-mind intervention should lead to improvement in behavioral and cognitive outcomes at post-intervention compared to baseline. |
| Secondary | | |
| This study aims to investigate the modulation effects of a novel body-mind intervention on brain outcomes. | Baseline and post-intervention assessments of brain outcomes (white matter, grey matter, functional connectivity in AD signature regions). | The novel body-mind intervention should lead to improvement in brain outcomes at post-intervention compared to baseline. |
| Tertiary/Exploratory | | |
| N/A | N/A | N/A |

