9 STATISTICAL CONSIDERATIONS

9.1 STATISTICAL HYPOTHESES

- Primary Endpoint(s):

We hypothesize that, compared to participants who receive a control intervention, participants who receive IBMT for improving behavior and cognition will have improved working memory, emotion regulation, and reduced subjective report of cognitive decline after completing the intervention at post-assessment, and will continue to show improvement 3 months after the intervention. Alternatively, our null hypothesis is that there will be no difference in the effects of IBMT for improving behavior and cognition and those of control intervention at post-assessment or after 3 months of intervention.

- Secondary Endpoint(s):

We hypothesize that, compared to participants who receive a RT control intervention, participants who receive IBMT for improving brain function and structure will have improved white matter, grey matter, and functional connectivity in AD-signature regions after completing the intervention at post-assessment, and will continue to show improvement 3 months after the intervention. Alternatively, our null hypothesis is that there will be no difference in the effects of IBMT for improving brain function and structure and those of RT at post-assessment or after 3 months of intervention.

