9.4 STATISTICAL ANALYSIS PLAN

9.4.1 GENERAL APPROACH

Behavioral and brain data analysis will undergo separate analyzing streams to test intervention effects and underlying mechanisms at different time points. Given the scope of this 1-year pilot project, the logical first step at this early stage of research is to examine the potential intervention effects and mechanisms in small sample size, then move to the full scale RCTs for replication. To address our study Aims, repeated-measures ANOVA will be used. By utilizing all assessment points, this approach allows for well-powered tests to detect significant differences in changes across the experimental conditions, even when assuming smaller magnitude effect sizes. Effect size measures (from the repeated-measures ANOVA, Cohen's d highlighting mean differences between treatment and control groups across assessments) will also be calculated to describe the intervention's effect on study outcomes.

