9.4.2 ANALYSIS OF THE PRIMARY ENDPOINT(S)

The primary endpoints are behavioral and cognitive assessments and are all repeated measures assessed at baseline, post-intervention, and 3-month follow-up. For cognitive assessment of N-Back working memory, percentage of correct trials will be calculated for each trial for all endpoints. For behavioral assessment of emotion regulation, mindfulness, and SCD, these self-report questionnaires will be calculated based on established scoring guides by summing all items within a given questionnaire for all endpoints. Next, the effects of intervention (IBMT vs. HE) on each of these primary endpoints will be examined using repeated-measures ANOVA with time x group interaction effect. Variance and covariance across repeated measures will be calculated as part of the ANOVA. Age and sex will be included as covariates to control for potential confounding effects of age and sex on behavioral and cognitive assessments. Results will be presented as F values for the interaction effect, along with p values to indicate statistical significance. Normality and homogeneity of variance assumptions will be checked using SPSS built-in tools for ANOVA. Because there are 4 primary endpoints, multiple comparison corrections will be conducted using FDR correction. Missing data will be handled with case-wise deletion.

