9.4.3 ANALYSIS OF THE SECONDARY ENDPOINT(S)

The secondary endpoints are brain assessments and are all repeated measures assessed at baseline, post-intervention, and 3-month follow-up. For brain assessment of white matter, white matter integrity metrics will be calculated for all endpoints based on standardized processing pipelines of diffusion-based white matter data using FSL (<http://www.fmrib.ox.ac.uk/fsl>). For brain assessment of grey matter, cortical thickness and volume metrics will be calculated for all endpoints based on standardized processing pipelines of structural MRI data using SPM12 (<http://www.fil.ion.ucl.ac.uk/spm>). For brain assessment of functional connectivity, pair-wise correlations of fMRI timeseries will be calculated for regions of interest and for all endpoints based on standardized processing pipelines of fMRI data using REST software (www.restfmri.net). After these data preprocessing and calculation, numerical values will be generated for all secondary endpoints (white matter, grey matter, and functional connectivity). Next, the effects of intervention (IBMT vs. HE) on each of these secondary endpoints will be examined using repeated-measures ANOVA with time x group interaction effect. Variance and covariance across repeated measures will be calculated as part of the ANOVA. Age and sex will be included as covariates to control for potential confounding effects of age and sex on brain function and structure. Results will be presented as F values for the interaction effect, along with p values to indicate statistical significance. Normality and homogeneity of variance assumptions will be checked using SPSS built-in tools for ANOVA. Because there are 3 secondary endpoints, multiple comparison corrections will be conducted using FDR correction. Missing data will be handled with case-wise deletion.

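### The primary time point is never named: Section 3 uses two visits, 9.4.2 and 9.4.3 test one interaction over three, and 9.1 claims effects at both later visits

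*Combined protocol and SAP*

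**What the plan says.** - **Section 3, primary row:** the endpoint is "Baseline and post-intervention assessments of behavioral and cognitive outcomes (emotion regulation, mindfulness, SCD"). The justification is that the intervention "should lead to improvement in behavioral and cognitive outcomes at post-intervention compared to baseline".
- **Section 3, secondary row:** "Baseline and post-intervention assessments of brain outcomes (white matter, grey matter, functional connectivity in AD signature regions"). The tertiary row is N/A, so the 3-month visit appears nowhere in the endpoint table.
- **Section 9.1:** the arms are hypothesised to differ at post-assessment, "and will continue to show improvement 3 months after the intervention". The null covers both times.
- **Section 9.4.1:** "By utilizing all assessment points, this approach allows for well-powered tests to detect significant differences in changes across the experimental conditions".
- **Section 9.4.2:** "The primary endpoints are behavioral and cognitive assessments and are all repeated measures assessed at baseline, post-intervention, and 3-month follow-up". Each endpoint gets one time-by-group interaction F from a repeated-measures ANOVA with age and sex as covariates, FDR correction over 4 endpoints, and case-wise deletion.
- **Section 9.4.3:** "The secondary endpoints are brain assessments and are all repeated measures assessed at baseline, post-intervention, and 3-month follow-up", with the same test and FDR over 3 endpoints.
- **Section 9.3:** the analysis set needs all 10 sessions and complete, usable primary-endpoint data.

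Post-intervention in Section 3 cannot naturally include the 3-month visit. Section 4.1 lists the two separately, and Section 1.3 places them at Visit 12 (Day 13 ±2) and Visit 13 (Day 90 ±2).

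**The concern.** The plan gives two definitions of its primary endpoint and a hypothesis that contains two claims, and it does not say which time point decides. Three things follow.

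1. A significant interaction over three visits does not say whether the arms differ at post-intervention, at 3 months, or at both. No time-specific contrast or follow-up test is specified.
2. Membership of the analysis set depends on which definition applies, because 9.3 and the case-wise deletion both turn on complete endpoint data.
3. If the choice stays open, it can be made after the results are known. Section 10.1.11 commits the trial to registration and results submission, where a time frame for the primary outcome will be needed.

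**Working it through.** **1. The plan's own power figure.** Section 9.2 states 80% power at N = 40, f = 0.3, alpha 0.05, and does not say how many visits this assumes. For the within-between interaction, λ = f²·N·m/(1−ρ), with df (m−1) and (N−2)(m−1). The correlations are the plan's behavioural range of .30 to .60.

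| Visits m | ρ | λ | Power |
|---|---|---|---|
| 2 | .30 | 0.09·40·2/0.70 = 10.29 | 87.8% |
| 2 | .60 | 0.09·40·2/0.40 = 18.0 | 98.5% |
| 3 | .30 | 0.09·40·3/0.70 = 15.43 | 94.1% |
| 3 | .60 | 0.09·40·3/0.40 = 27.0 | 99.7% |

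Neither definition reproduces 80%, so the sample-size section does not reveal which one was intended. The mismatch itself is a separate matter.

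**2. What the three-visit F responds to.** Inputs: 18 per arm (Section 5.5: 36 completers, split equally) and compound symmetry. The arm differences in SD units are assumptions, because the plan gives none. With δ the arm difference at each visit and δ̄ its mean over visits, λ = (n/2)·Σ(δ−δ̄)²/(1−r). For r = .60 and 0.6 SD:

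- Effect sustained (0, 0.6, 0.6): Σ = 0.24, λ = 9·0.24/0.40 = 5.4.
- Effect gone by Day 90 (0, 0.6, 0): Σ = 0.24, λ = 5.4.
- Effect only at Day 90 (0, 0, 0.6): Σ = 0.24, λ = 5.4.
- Effect halved (0, 0.6, 0.3): Σ = 0.18, λ = 4.05, on 2 df.
- Two-visit test (0, 0.6): Σ = 0.18, λ = 4.05, on 1 df.

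The F test has the same power, about 51-52%, for the first three patterns, so it cannot separate the two claims in 9.1. With a halved effect it has the same λ as the two-visit test but spends an extra degree of freedom, hence the lower power. With a sustained effect the larger λ offsets that cost.

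**3. Power and disagreement.** 20,000 simulated trials per setting; 18 per arm; alpha 0.05; no covariates, no FDR, no missing data. The two-visit test is the group comparison of change from Visit 1 to Visit 12. Cells show two-visit power / three-visit power / trials in which only one test rejects (%).

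| Pattern | r .30, 0.6 SD | r .30, 0.8 SD | r .60, 0.6 SD | r .60, 0.8 SD |
|---|---|---|---|---|
| Sustained | 32 / 32 / 16 | 50 / 52 / 18 | 50 / 52 / 18 | 74 / 78 / 15 |
| Halved | 32 / 25 / 13 | 51 / 41 / 15 | 50 / 40 / 15 | 74 / 65 / 13 |
| Gone by Day 90 | 31 / 32 / 15 | 50 / 53 / 18 | 50 / 51 / 18 | 74 / 78 / 14 |

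With no effect, each test rejects in about 5% of trials and they disagree in about 5%. With 0.6 SD only at Day 90, the two-visit test rejects in 5% and the three-visit test in 32% (r .30) or 51% (r .60). Repeat simulations put the lowest disagreement under a post-intervention effect at 12%.

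**4. Participants.** Section 5.5 plans 4 dropouts of 40 and gives no timing. If all 4 leave after Visit 12, the Section 3 endpoint exists for 40 and 9.4.2 analyses 36. If all 4 leave during the sessions, both analyse the same 36. If each person has an assumed chance p of missing only Visit 13, the chance that the two sets differ is 1−(1−p)^40: 64% for p = 2.5%, 87% for 5%, 98.5% for 10%. With 20 per arm, 4 missing at Visit 13, r = .60 and an effect halving from 0.6 SD, power is 54% (two visits) against 40% (three), and decisions differ in 20% of trials. With nobody missing they differ in 14%.

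**5. A test aimed at Visit 12.** Adjusting Visit 12 for Visit 1 gives λ ≈ (n/2)·d²/(1−r²). For 0.6 SD this is 9·0.36/0.91 = 3.56 (r .30) and 9·0.36/0.64 = 5.06 (r .60). Simulated power was 44% and 57%, against 31% and 52% for the three-visit F with a sustained effect. Much of this gain comes from the baseline adjustment: the plain change test has about the same power as the three-visit F here.

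**The case against.** Section 3 is the outlier. Sections 1.3, 4.1 and 8.1 schedule three assessments, 9.1 hypothesises about both later ones, and 9.4.1 says that all are used. On that view Section 3 merely omits the 3-month visit, and adding it would reconcile the text. The pattern closest to 9.1 is a sustained effect, for which the three-visit test loses nothing. The trial is also described as an exploratory pilot, with Cohen's d reported alongside p values.

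The description of Section 3 stands, and so does the point on power. Adding a visit to Section 3 would align the wording, but the single F would still be unable to tell a lasting effect from one that has gone by Day 90. The reported d values describe group differences and do not supply the missing time-specific test.

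A reader might infer more than the documents support:

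- **That the two definitions analyse different people.** This is conditional. It needs someone to complete Visit 12 and miss Visit 13, and 9.3 already removes anyone short of 10 sessions under both definitions.
- **That the three-visit test is generally weaker.** It is weaker only under an assumed fading effect such as halving.
- **That the decisions often conflict.** The rate is 12-18% per endpoint under assumed effects and about 5% under none.
- **That the post-intervention endpoint is never tested in those who have it.** If everyone attends Visit 13, the same people are analysed and only the contrast differs.

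**Conclusion.** The inconsistency is real, covers both the primary and secondary endpoints, and is not resolved anywhere in the plan. Its firmest consequence needs no assumed effect size: under compound symmetry, one three-visit interaction F cannot say at which visit the arms differ, although 9.1 makes a claim about each. The other consequences are conditional. The loss of participants is 0 to about 4 of 40, depending on when dropout occurs. The disagreement and power figures rest on assumed effects and time courses, the plan's behavioural correlations, compound symmetry, 18 per arm, and no covariates or FDR. This should be corrected before analysis. Because the trial is an exploratory pilot, it does not undermine the design.

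**What to change.** - **Section 3:** name post-intervention (Visit 12) as the primary time point. Add N-Back to the listed measures: the row names three, while 9.4.2 counts 4 and 9.1 hypothesises on working memory. List 3 months as a separate maintenance endpoint.
- **Section 9.4.2:** test the IBMT-HE difference at Visit 12, adjusted for the Visit 1 value, age and sex, without requiring Visit 13. Apply the FDR correction to these 4 tests. Give 3 months its own baseline-adjusted test.
- **Section 9.4.3:** mirror this for the 3 brain endpoints.
- **Sections 9.1, 9.3 and 9.4.1:** split the hypothesis into a primary and a maintenance part; define complete primary data as Visits 1 and 12; amend the statement that the tests use all assessment points.

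The cost is wording in six sections and no new data. The downside is that an effect seen only at Day 90 would not count as success on the primary endpoint.
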